Attachment 5. Protocol JPBA Recommendations for Reporting Serious Adverse Events

Recommendations for Reporting Serious Adverse Events

When telephoning the Lilly office to report a serious adverse event, please have the following information available:

Patient Demographics

- patient identification (number)
- sex
- date of birth
- race
- height & weight

Study Identification

- full trial protocol number
- investigator's name
- investigator's number

Study Drug

- drug code or drug name
- unit dose
- total daily dose
- frequency
- route
- start dose
- cycle details
- start date & last dose date (if applicable)

(continued)

Adverse Event

- description
- date of onset
- severity
- treatment (including hospitalization)
- action taken with respect to study drug
- clinical significance
- test & procedure results (if applicable)

Relationship to Study Drug & Protocol Procedures**Concomitant Drug Therapy**

- indication
- total daily dose
- duration of treatment
- start date
- action taken

In Case of Death

- cause
- autopsy finding (if available)
- date
- relationship to study drug & protocol procedures.

Attachment 6. Protocol JPBA ECOG Performance Status

Eastern Cooperative Oncology Group (ECOG) Performance Status

| Activity Status | Description |
|-----------------|---|
| 0 | Fully active, able to carry on all pre-disease performance without restriction. |
| 1 | Restricted in physically strenuous activity but ambulatory and able to carry out work of a light or sedentary nature (for example, light housework, office work). |
| 2 | Ambulatory and capable of all self-care but unable to carry out any work activities. Up and about more than 50% of waking hours. |
| 3 | Capable of only limited self-care, confined to bed or chair more than 50% of waking hours. |
| 4 | Completely disabled. Cannot carry on any self-care. Totally confined to bed or chair. |
| 5 | Dead. |

Source: Oken et al. 1982.

Attachment 8. Protocol JPBA Inducers and Strong Inhibitors of CYP3A

The information in this Attachment is provided for guidance to investigators and does not preclude the use of these medications if clinically indicated.

Strong Inducers of CYP3A

Carbamazepine
Dexamethasone*
Phenobarbital/phenobarbitone
Phenytoin
Rifapentine
Rifampin
Rifabutin
St. John's wort

Moderate Inducers of CYP3A

Bosentan
Lesinurad
Modafinil
Primidone
Telotristat ethyl

Strong Inhibitors of CYP3A

Aprepitant
Ciprofloxacin
Clarithromycin
Conivaptan
Diltiazem
Erythromycin
Fluconazole
Itraconazole
Ketoconazole
Nefazodone
Posaconazole
Troleandomycin
Verapamil

*Important note: Patients with glioblastoma multiforme or brain metastases may receive acute or chronic therapy with dexamethasone, if clinically indicated. All patients may receive supportive therapy with dexamethasone, preferably ≤7 days, if clinically indicated.

**Attachment 9. Protocol JPBA
Protocol Amendment I3Y-MC-JPBA(j) Summary
Phase 1 Study of a CDK4/6 Dual Inhibitor in Patients with
Advanced Cancer**

Overview

Protocol I3Y-MC-JPBA, a Phase 1 Study of a CDK4/6 Dual Inhibitor in Patients with Advanced Cancer has been amended. The new protocol is indicated by amendment (j) and will be used to conduct the study in place of any preceding version of the protocol.

Modifications to the study protocol introduced in amendment (j) involve the following:

- The Rationale for Amendment (j) was added as Section 4.4.
- Table JPBA.6.2 was updated with dose adjustment criteria for nonhematologic toxicity and ALT/AST increased.
- Information for modulators of CYP3A and transporter substrates was updated in the section for Concomitant Therapy (Section 6.5).
- The Hepatic Monitoring guidance in Section 7.1.3.1 was updated based on current information.
- The safety monitoring language for VTEs in Section 7.1.3.3 was updated.
- Section 7.1.3.4 was edited slightly for clarity to include specific ILD/pneumonitis Grades requiring LY2835219 discontinuation.

Minor typographical and formatting edits were made throughout the document for clarity and consistency

Leo Document ID = 6da9678e-c557-4307-8091-269b1c14a618

Approver:PPD

Approval Date & Time: 26-Feb-2021 01:55:10 GMT

Signature meaning: Approved

Approver:PPD

Approval Date & Time: 26-Feb-2021 13:50:11 GMT

Signature meaning: Approved

### 3. Revision History

Statistical Analysis Plan (SAP) Version 1 was approved on February 17, 2010 prior to unblinding.

Statistical Analysis Plan Version 2 was created based on Protocol I3Y-MC-JPBA (JPBA) Amendment (c). Protocol JPBA Amendment (c) added a new dosing schedule, receiving study drug every 12 hours for Days 1 through 28 of a 28-day cycle to the study. It also added Melanoma patients in the tumor-specific expansion phases.

Statistical Analysis Plan Version 3 was created based on Protocol JPBA Amendments (f) and (g). This SAP includes the definitions of the analysis populations, the pharmacokinetics (PK), the pharmacodynamic (PD), efficacy and safety endpoints, the tables, listings and graphs for the analysis. It is based on Protocol JPBA Amendments (f) and (g) approved on the 14 December 2012 and 29 August 2013. Protocol JPBA Amendment (f) added a colorectal cohort in the tumor-specific expansion phases. It also allowed expansions up to 45-60 patients in each tumor-specific expansion if approved by the sponsor. Protocol JPBA Amendment (g) added a hormone receptor positive breast cancer cohort.

## 4. Study Objectives

### 4.1. Primary Objective

The primary objective of this study is to evaluate the safety and tolerability of LY2835219 when administered orally to patients with advanced cancer.

### 4.2. Secondary Objectives

The secondary objectives of this study are to:

- Determine the PK of LY2835219
- Evaluate PD and predictive biomarkers
- Document the antitumor activity of LY2835219
- Establish a recommended dose range for Phase 2 studies.

## 5. Investigational Plan

This study is a multicenter, nonrandomized, open-label, dose-escalation Phase 1 trial of LY2835219 in approximately 100 patients with advanced cancer.

For the original schedule, patients will continue to receive LY2835219 orally every 24 hours. For the new schedule, patients will receive LY2835219 orally every 12 hours for Days 1 through 28 of a 28-day cycle (refer to [Figure JPBA.5.1](#)). There are modifications during cycle 1 to enable PK sampling following a single dose and repeated doses.

Patients will be enrolled in cohorts of 3 patients at each planned dose levels (Part A). Patients will receive 2 cycles of LY2835219 unless one or more of the criteria for discontinuation (Protocol JPBA Section 2.3.1) are fulfilled; the follow-up period for post-study evaluation will be  $30\pm7$  days from the date of the last dose of study drug received. A patient may receive more than 2 cycles of treatment only if 1) none of the criteria for discontinuation have been fulfilled, and 2) the investigator, in consultation with the Eli Lilly and Company (Lilly) clinical research physician (CRP), determines that the patient is experiencing clinical benefit from treatment.

During dose escalation (Part A), 33 patients were treated across 2 schedules. For the once daily schedule, patients were treated at 50, 100, 150, and 225 mg every 24 hours (Q24H). For the twice daily schedule, patients were treated at 75, 100, 150, 200, and 275 mg every 12 hours (Q12H). A maximum tolerated dose (MTD) for the once daily schedule was not reached whereas the MTD for the twice daily schedule was tentatively established (pending dose confirmation) at 200 mg Q12H. As depicted in [Figure JPBA.5.1](#), the study design consists of a dose escalation phase (Part A) and 6 tumor-specific expansion phases (Parts B, C, D, E, F, and G). The dose escalation phase (Part A), described in Protocol Section 6.2.2, was guided by safety assessments from Days 1 through 28 of Cycle 1 for all patients in the cohort and also by the emerging PK data. Dose escalation occurred until the MTD (defined in Protocol Section 6.2.2.1) was determined for at least 1 schedule.

After the last patient enrolled in the dose escalation phase (Part A) completes Cycle 1, then the 6 tumor-specific expansion phases (Parts B, C, D, E, F, and G) may begin. In each tumor-specific expansion phase, at least 15 and up to 45-60 patients will be treated on the twice daily schedule at a dose no greater than the MTD (200 mg every 12 hours) with administration of LY2835219 on Days 1 through 28 of a 28-day cycle, with modifications during Cycle 1 to enable PK sampling following a single dose and repeated doses.

[figure not shown]

Figure JPBA.5.1. Study design for I3Y-MC-JPBA.

## 6. A Priori Statistical Methods

### 6.1. Derived Endpoint Definitions

#### 6.1.1. Safety Endpoints

Safety measures that will be recorded in the study include adverse events (AE), dose limiting toxicities (DLT), DLT equivalent toxicity, laboratory test results, vital signs, electrocardiogram (ECG) and Eastern Cooperative Oncology Group (ECOG) performance status. All AEs will be graded using the National Cancer Institute Common Terminology Criteria for Adverse Events, CCI [REDACTED] NCI CTCAE CCI.

##### Dose Limiting Toxicity and Equivalent Toxicity

Dose-limiting toxicity is defined as an AE occurring between Day -3 and Day 28 of Cycle 1 for a patient enrolled in Part A that is possibly related to the study drug and fulfills any one of the following criteria:

- Grade 3 or 4 non-hematological toxicity according to the NCI Common Terminology Criteria for Adverse Events (CTCAE CCI) except for nausea, vomiting, diarrhea, or electrolyte disturbance.
- Grade 3 or 4 nausea, vomiting, diarrhea, or electrolyte disturbance that persists more than 2 days despite maximal supportive intervention.
- Grade 4 hematological toxicity that persists more than 5 days.
- Grade 3 or 4 thrombocytopenia with bleeding.
- Grade 3 or 4 neutropenia with fever.

Investigators, together with the Lilly CRP, can declare a DLT if a patient is experiencing increasing toxicity during treatment, and it becomes clear that it is not going to be possible to complete the treatment without exposing the patient to excessive risk. In this case, the remaining treatment has to be suspended and a DLT declared. In Part A (Cycle 1 only), AEs mentioned above that are possibly related to study medication are designated a DLT; by contrast, in Part A (Cycle 2 and beyond) and in Parts B, C, D, E F, and G (regardless of cycle), similar events are designated dose-equivalent toxicities.

##### Maximum Tolerated Dose

Maximum tolerated dose (MTD) is defined as the highest study dose level at which less than 33% of patients experience a DLT during Part A Cycle 1. If DLT (or DLT equivalent-toxicity) occurs in 33% or more of patients within a tumor-specific cohort expansion, then investigators and the Lilly CRP will assess the nature and severity of these toxicities. No additional patients will be accrued until this safety review is completed and a decision is made either to continue at the current dose or to deescalate the dose and define a new dose for the expansion phase.

### Biologically Effective Dose

Biologically effective dose (BED) is estimated using the PK and PD data. For the purpose of this study, the BED is defined as the lowest dose that achieves a minimum of 30% to 50% inhibition of CDK4/6 (measured by pRb and topoII $\alpha$ ) in surrogate tissues (hair follicles or skin) at steady state throughout the duration of the treatment.

#### **6.1.2. Efficacy Endpoints**

Efficacy assessments will be derived for patients during the Dose Confirmation Phase (Part B, C, D, E, F, and G).

Response (Complete Response [CR] and Partial Response [PR]) and progression (Stable Disease [SD] and Progressive Disease) for tumors will be evaluated using the Response Evaluation Criteria in Solid Tumors (RECIST) Version 1.1 (Eisenhauer et al. 2009), with the notable exception that response and progression for lymphomas will be evaluated using the Revised Response Criteria for Malignant Lymphoma (Cheson et al. 2007).

The Best Overall Response is the best response recorded by the investigator from the start of the treatment until the end of treatment taking into account any requirement for confirmation. Any radiological assessment that occurs within seven days of the end of treatment will also be included in this evaluation.

All lesion assessments, whether by physical exam or radiological methods, should be repeated by the same method at least 4 weeks following the initial observation of an objective response to ensure response confirmation. In the case of SD, follow-up measurements must have met the SD criteria at least once after study entry at a minimum interval of not less than 6 to 8 weeks. If a patient is discontinued from the study, repeat radiology may be omitted if there are clear clinical signs of progressive disease.

The Duration of Overall Response is measured from the time measurement criteria are first met for CR/PR (whichever is first recorded) until the first date that recurrent or progressive disease is objectively documented (taking as reference for progressive disease the smallest measurements recorded since the treatment started).

The Duration of Overall CR is measured from the time measurement criteria are first met for CR until the date that recurrent disease is objectively documented.

The Duration of Stable Disease is measured from the start of the treatment until the criteria for progression are met, taking as reference the smallest measurements recorded since the treatment started.

Progression-Free Survival (PFS) time is defined as the time from the date of first day of study drug to the first date of progressive disease (symptomatic or objective) or death due to any cause, whichever occurs first. For patients who are not known to have died or progressed as of the data-inclusion cutoff date, PFS time will be censored at the date of the last objective progression-free disease assessment prior to the date of any subsequent anticancer therapy.

Overall Survival (OS) time is defined as the time from the date of first day of study drug to the date of death from any cause. For patients not known to have died as of the data cut-off date, OS time will be censored at the last contact date the patient was known to be alive prior to the cut-off date.

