7.3. Efficacy Evaluations

A secondary objective of the study is to document any antitumor activity. Refer to [Attachment 1](#) for details regarding the timing of specific efficacy measures.

Each patient will be assessed by one or more of the following radiologic tests for tumor measurement:

- Computerized tomography (CT) scan
- Magnetic resonance imaging (MRI) scan
- Chest x-ray

Each patient's full extent of disease will also be assessed with the following procedures:

- Tumor measurement of palpable or visible lesions (refer to RECIST 1.1)
- Evaluation of tumor markers, if indicated.
- Evaluation of performance status (refer to the ECOG Scale, [Attachment 6](#)).

All lesion assessments, whether by physical exam or radiological methods, should be repeated by the same method at least 4 weeks following the initial observation of an objective response to

ensure response confirmation. If a patient is discontinued from the study, repeat radiology may be omitted if there are clear clinical signs of progressive disease. CT scans and MRIs may be requested to be sent to an off-site storage facility, and potentially independently reviewed and/or read by Lilly or its designee.

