9.2. Efficacy

Response and progression for tumors will be evaluated using the Response Evaluation Criteria in Solid Tumors (RECIST) Version 1.1 (Eisenhauer et al. 2009), with the notable exception that response and progression for lymphomas will be evaluated using the Revised Response Criteria for Malignant Lymphoma (Cheson et al. 2007).

Tumor response and time-to-event data will be tabulated. For each expansion cohort, the time-to-event data analysis will include calculation of 6-month progression-free survival probability. Any patient that discontinues due to a reason other than progressive disease or death (for example, AE, patient/investigator decision) will have their time-to-event data either censored at Visit 801 if no progressive disease is found during this visit, or censored at the date of the last objective progression-free disease assessment if progressive disease is found at Visit 801.

For Part G, patients may have already received 1 or more cycles of fulvestrant prior to study enrollment. This prior therapy confounds the interpretation of response and progression. As a result, tabulations of tumor response and time-to-event data will be considered descriptive only.

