- g Imaging studies are performed locally. Radiological tumor assessment is performed at baseline (Day -28 to Day-4), then between Day 21 and Day 28 (inclusive) of every other cycle beginning with Cycle 2; if necessary, radiological tumor assessment between Day 21 and Day 28 may be extended to Day 29 or Day 30 if the Day 28 procedures occur on Day 29 or Day 30, respectively (refer to footnote p for additional information). For patients with glioblastoma multiforme who are receiving corticosteroids (for example, dexamethasone), the baseline imaging study should be performed on a stable dose of corticosteroids. For patients with glioblastoma multiforme or brain metastases, radiological tumor assessment should also include MRI scan (preferred) or CT scan of the brain.
- h If a patient is discontinued from the study, repeat radiology may be omitted if progressive disease can be documented quantitatively with clinical measurements.
- i Request archived paraffin-embedded tumor tissue (to be used for assessment of tumor Rb and p-Rb status), but only after study eligibility is confirmed.
- j Only for patients in Parts B, C, D, E, F, and G. Pre-treatment biopsy should be obtained (whenever clinically feasible) between Day -14 and Day -4, but only after study eligibility is confirmed. Posttreatment biopsy should be obtained (whenever clinically feasible) between Day 8 and Day 22. Greater flexibility has been provided for the post-treatment tumor biopsy (15 ± 7) compared to other Day 15 assessments (15 ± 2) to enable radiographic guidance and access to appropriate medical specialists.
- k For central versus local labs, refer to [Attachment 2](#).

- o Follow-up starts just after the last dose of study drug and ends when final safety assessments are completed (30 ± 7 days after last dose of study drug).
- p If Day 28 procedures occur on Day 29 or 30, then these procedures are included in the current cycle and initiation of the next cycle is delayed until the following day.
- q For patients already receiving fulvestrant at time of study entry, fulvestrant dose on Cycle 1 Day 1 should correspond approximately to the date of its expected monthly administration.
- r For patients already receiving fulvestrant at time of study entry, fulvestrant should not be administered on Cycle 1 Day 15.

Continued Access Assessments

| Cycle/Visit | Cycles 501-5XX | | Continued Access Follow-up (901) | Comments |
|---|----------------|-------|----------------------------------|---|

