### **6.3.9. Efficacy**

Efficacy assessments will be derived for patients during Dose Confirmation Phase (Parts B, C, D, E, F, and G).

Eastern Cooperative Oncology Group performance status (PS) will be listed and summarized for patients on therapy by cohort and cycle.

Reported lesion data (target or non-target) and investigator evaluation will be listed for patients on therapy.

Tumor markers will be listed for patients on therapy.

The best overall response, duration of overall response, duration of overall CR and duration of SD will be listed for patients on therapy. If appropriate, the efficacy endpoints, including Overall Response Rate, Disease Control Rate, Duration of Overall Response, Duration of

Overall CR, Duration of Stable Disease, PFS, and OS, will be summarized for Parts B, C, D, E F, and G.

The Overall Response Rate is defined as the proportion of patients who exhibits a confirmed CR or PR relative to baseline as defined by RECIST Version 1.1 (Eisenhauer et al. 2009). A responder is defined as any patient who exhibits a confirmed CR or PR relative to baseline assessment.

Disease Control Rate is defined as the proportion of patients in the analysis population who exhibit a SD or confirmed CR or PR relative to baseline during the study. Response is defined by RECIST Version 1.1 (Eisenhauer et al. 2009).

Overall Response Rate and Disease Control Rate with their respective 95% CI will be estimated using the Clopper-Pearson method. For time to event endpoints, including Duration of Overall Response, Duration of Overall CR, Duration of Stable Disease, PFS, and OS, the survival curve will be estimated by the Kaplan-Meier method (Kaplan and Meier 1958). Quartiles and rates at time points of every 3 months, together with the 95% CIs, will be provided.

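### As SAP 6.1.2 reads, a response cannot be confirmed if treatment ends less than 21 days after the first CR/PR scan

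*SAP*

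**What the plan says.** Three rules in the SAP bear on the same patient.

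- **Window.** SAP 6.1.2: "The Best Overall Response is the best response recorded by the investigator from the start of the treatment until the end of treatment", allowing for any confirmation requirement. The next sentence extends it: "Any radiological assessment that occurs within seven days of the end of treatment will also be included in this evaluation".
- **Confirmation.** SAP 6.1.2 has lesion assessments repeated "at least 4 weeks following the initial observation of an objective response to ensure response confirmation". Protocol 7.3 has the same interval and no seven-day limit. Both let repeat radiology be dropped after discontinuation when progression is clinically evident.
- **Who counts.** SAP 6.3.9: "A responder is defined as any patient who exhibits a confirmed CR or PR relative to baseline assessment". SAP 6.2 puts every patient with at least one dose in the efficacy population.

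The disease control rate in SAP 6.3.9 also requires CR or PR to be confirmed, but refers to the study period rather than to the treatment period. The ORR definition gives no window.

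For timing, Protocol Attachment 1 (footnote g) schedules radiology at baseline, "then between Day 21 and Day 28 (inclusive) of every other cycle beginning with Cycle 2". Protocol 5.2 plans two 28-day cycles, with more only if there is clinical benefit, and a follow-up visit 30 ± 7 days after the last dose.

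**The concern.** The window closes 7 days after treatment ends, while confirmation cannot happen until 28 days after the response is first seen. For a patient who stops soon after that first scan, no assessment can satisfy both.

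The patient affected is one who leaves treatment while still responding, for example because of an adverse event or by their own decision. The plan foresees such exits: Protocol Table JPBA.6.2 makes discontinuation mandatory for some toxicities, and SAP 6.3.11 describes expansion patients who stop for an adverse event and complete follow-up. Because repeat radiology may be skipped only when progression is clinically evident, this patient is still expected to have the repeat scan. On the natural reading of SAP 6.1.2 that scan is then not used.

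At stake is the ORR in Parts B to G, the measure of antitumor activity on which Protocol 9.1.1 sizes the expansions. The error runs in one direction: a true responder becomes a non-responder and stays in the denominator.

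**Working it through.** **The plan's own figure.** Protocol 9.1.1 states about 85% power for 40% against 5% ORR with 45 patients, and for 34.5% against 5% with 60, in equal marker groups. The visible text does not give the test or the alpha. Assuming Fisher's exact test at one-sided 0.05, enumeration gives 85.5% (22 marker-present, 23 marker-absent) or 84.2% (23/22) for 45 patients, and 85.8% (30/30) for 60. The stated figure is reproduced.

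**Timing.** Let R be the day of the first CR/PR scan and E the day treatment ends.

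- Earliest confirming assessment: R + 28 (4 weeks; SAP 6.1.2, Protocol 7.3).
- Last assessment that counts: E + 7 (SAP 6.1.2).
- Confirmation is possible only if E + 7 ≥ R + 28, that is E ≥ R + 21.
- Check: with E = R + 20 the last countable day is R + 27, one day short.

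**Stopping at the end of Cycle 2.** The first on-treatment scan falls on Days 21 to 28 of Cycle 2, so 0 to 7 days before Day 28. The last countable day is then 7 to 14 days after that scan, below 28.

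**Scheduled scans only.** On a continuous 28-day count the Cycle 2 window is days 49 to 56 and the Cycle 4 window is days 105 to 112. The gap is 105 − 56 = 49 to 112 − 49 = 63 days. Less the 7-day allowance, the patient must stay on treatment 42 to 56 days after the first response, unless an extra repeat scan is done.

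**Follow-up visit.** 30 ± 7 gives 23 to 37 days after the last dose, wholly beyond the 7-day allowance. If the response scan was on the last dosing day, a visit on days 23 to 27 would also be too early to confirm.

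**Size per patient.** 1/15 = 6.7 points, 1/45 = 2.2 points, 1/60 = 1.7 points of ORR.

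**Illustration only.** The documents give no share of responders lost. Assuming the same share is lost in both marker groups, with the test assumed above:

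| Share lost | 45 (22/23) | 45 (23/22) | 60 (30/30) |
|---|---|---|---|
| 0% | 85.5% | 84.2% | 85.8% |
| 5% | 83.0% | 81.1% | 83.1% |
| 10% | 80.2% | 77.5% | 80.0% |
| 20% | 73.9% | 69.1% | 72.5% |
| 30% | 66.5% | 59.0% | 63.1% |

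SAP 6.3.1 plans no p-values, so this only gives a sense of scale.

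**The case against.** **The exclusion is inferred.** SAP 6.1.2 says which later scans are included and never says that others are discarded for confirmation. One could read the window as governing which response may be called best, with confirmation judged under its own paragraph. The ORR text does not repeat the limit. This stands as a limit on how firmly the point can be put. It does not remove it: an extension of seven days has little purpose if later scans count anyway, and a programmer following the text would stop there. The confirmation clause in the window sentence adds a condition without lengthening the window.

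**An on-treatment window is a legitimate choice.** It avoids crediting the drug with off-drug images. That supports limiting when a response may first be seen. It is a weaker reason for refusing to confirm one already seen on drug.

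**Few patients are affected.** Most toxicities in Protocol Table JPBA.6.2 lead to suspension or dose reduction, and patients with clinical benefit may continue past Cycle 2. Those who stop for progression would normally fail confirmation anyway. As far as the schedule table can be read, no radiology is set at follow-up, so a late confirmation depends on the repeat scan in Protocol 7.3. All of this stands. Lesion data are also listed by patient, so a late confirmation that was collected would be visible.

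**Protocol 9.2 is not a contradiction.** It has time-to-event data "censored at Visit 801 if no progressive disease is found during this visit", but that concerns censoring, a different endpoint. It shows only that the protocol uses disease status at that visit.

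**Conclusion.** The point holds as a drafting fault with a directional effect. Read as written, a patient whose treatment ends less than 21 days after the first CR/PR scan, without progression, cannot be a confirmed responder. The response windows for best overall response, ORR and disease control are also not aligned. The conclusion rests on reading the 7-day sentence as a cut-off and on taking 4 weeks as 28 days. SAP 6.1.2 does not define the end of treatment.

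The consequence is limited. Antitumor activity is a secondary objective, the analyses are descriptive, and no primary result or stated sample size is wrong.

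A reader might infer more than the documents support:

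- *That these patients also drop out of duration of response.* SAP 6.1.2 starts that duration when CR/PR criteria are first met and does not restrict it to confirmed responders.
- *That ORR is biased most in the least tolerant cohorts, mainly through toxicity.* This is plausible, but no figures are given.
- *That one lost responder should be set against a 5% threshold.* The 5% in Protocol 9.1.1 is the assumed ORR of the marker-absent group, not a decision limit for a whole cohort.
- *That the SAP expressly discards the late scan.* It does so by implication only.

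**What to change.** In SAP 6.1.2:

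1. Keep end of treatment plus 7 days as the window for the first observation of CR or PR.
2. Add that a repeat assessment at least 4 weeks later confirms that response even if taken more than 7 days after treatment ends, provided it precedes documented progression and any subsequent anticancer therapy.
3. Do not close this at Visit 801, since a visit less than 28 days after the response scan would shut out a valid later confirmation.
4. Apply the same rule to best overall response, ORR and disease control in SAP 6.3.9, define the end of treatment, and say how a CR or PR that is never confirmed is classified.

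The cost is the added SAP wording and a change to the response derivation. No visit or scan is needed beyond the repeat assessment Protocol 7.3 already asks for, and the stated sample size and power do not change. The small downside is that a few confirmations will rest on off-drug images, which can be flagged in the listing.

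### The three SAP duration endpoints do not name death as an event or give a censoring rule, so under Kaplan-Meier a death without documented progression can only be censored

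*SAP*

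**What the plan says.** SAP 6.1.2 gives each duration its own end point:

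- Duration of Overall Response runs from first CR or PR "until the first date that recurrent or progressive disease is objectively documented".
- Duration of Overall CR runs from first CR "until the date that recurrent disease is objectively documented".
- Duration of Stable Disease is "measured from the start of the treatment until the criteria for progression are met".

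Death appears in none of them. The same section defines PFS as time from first dose to "progressive disease (symptomatic or objective) or death due to any cause, whichever occurs first". It then gives PFS a censoring rule: "For patients who are not known to have died or progressed as of the data-inclusion cutoff date, PFS time will be censored" at the last objective progression-free assessment before any new anticancer therapy. OS has its own rule. The three durations have none.

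SAP 6.3.9 groups them for analysis: "For time to event endpoints, including Duration of Overall Response, Duration of Overall CR, Duration of Stable Disease, PFS, and OS" are estimated by Kaplan-Meier, with quartiles and rates every 3 months and 95% CIs.

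Protocol 9.2 has a general censoring rule for time-to-event data, limited to patients who discontinue for a reason other than progression or death. They are censored at Visit 801 if no progression is found there, or at the last objective progression-free assessment if it is.

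**The concern.** A Kaplan-Meier observation is either an event or censored. If death is not an event, a responder who dies between assessments is handled as someone whose response might have continued, and the curve does not step down for that patient. How long responses and disease stabilisation last is part of the secondary objective of documenting antitumor activity, and the quartiles and 3-monthly rates are the figures that will be reported for it.

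The clearest inconsistency is between Duration of Stable Disease and PFS. One starts at start of treatment, the other at first dose of study drug. A stable-disease patient who dies without documented progression is a PFS event, but not a Duration of Stable Disease event, over essentially the same interval.

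Such deaths are plausible. Parts B to F enrol patients for whom standard therapy has stopped helping. Dose confirmation allows ECOG status up to 2, and the life-expectancy criterion is 12 weeks. Imaging falls in every other 28-day cycle from Cycle 2, about every 8 weeks.

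**Working it through.** **The plan's own figure.** There is none to reproduce. Neither document gives an expected median duration, an event count or a share of deaths for these endpoints.

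**Step 1: how one death is handled.** Take a patient who dies without documented progression.

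| Endpoint (SAP 6.1.2) | Event? | Censoring rule given? |
|---|---|---|
| PFS | Yes | Yes, for patients without an event |
| OS | Yes | Yes, for patients without an event |
| Duration of Overall Response | No | None |
| Duration of Overall CR | No | None |
| Duration of Stable Disease | No | None |

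The protocol 9.2 rule does not reach a patient who discontinues because of death, so it does not fill the last three rows.

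**Step 2: direction.** If the death is censored on its own date, the risk set before that date is unchanged and one downward step is removed. The curve is then the same or higher throughout. The SAP does not say which date would be used.

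**Step 3: size, for illustration only.** Let progression and death without documented progression have constant, independent hazards p and d, with total h = p + d, and let f = d/h be the share of first events that are such deaths.

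- Death counted: median = ln 2 / h.
- Death censored: median = ln 2 / p = ln 2 / [(1 − f)h], which is the first median divided by (1 − f).
- Survival at any time t changes from S(t) to S(t)^(1 − f).

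With an assumed median of 6.0 months with death counted (so a 6-month rate of 50%):

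| f (assumed) | Factor 1/(1 − f) | Median, months | 6-month rate |
|---|---|---|---|
| 0% | 1.00 | 6.0 | 50.0% |
| 10% | 1.11 | 6.7 | 53.6% |
| 20% | 1.25 | 7.5 | 57.4% |
| 30% | 1.43 | 8.6 | 61.6% |

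The percentage change in the median (+11%, +25%, +43%) does not depend on the 6.0 months.

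**Step 4: cohorts of the planned size.** Under the design assumptions in protocol 9.1.1 with equal marker groups, expected responders are 22.5 × 0.40 + 22.5 × 0.05 = 10.1 for 45 patients, and 30 × 0.345 + 30 × 0.05 = 11.9 for 60. One such death is therefore roughly 8% to 10% of the responders.

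A simulation used 12 responders, a true median of 6 months with death counted, follow-up uniform on 12 to 24 months, 3,000 runs, and deaths censored on their date. It gave these typical Kaplan-Meier medians:

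| f | Death counted, months | Death censored, months | Runs with a longer median |
|---|---|---|---|
| 10% | 5.4 | 6.2 | 46% |
| 20% | 5.4 | 7.3 | 75% |
| 30% | 5.3 | 8.5 | 88% |

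The median with deaths censored was never shorter. At f = 10% it was unchanged in about half the runs, so a single cohort need not show the effect.

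**The case against.** The strongest reply is that the SAP nowhere says deaths are censored. It gives these durations no censoring rule, and protocol 9.2 sets death beside progression as outside its own rule. That stands, and it limits the point: censoring follows from applying the definitions literally and is not a written instruction. It does not rescue the plan, because no passage makes death an event for these durations. The handling is either literal censoring or undefined.

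A reader might infer several stronger things that the documents do not support:

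- *That these patients are dropped.* Censored patients stay in the risk set until their censoring date.
- *That every responder who dies without a progression scan must be censored.* SAP 6.1.2 accepts lesion assessment by physical examination, and the protocol's study schedule accepts progression documented by clinical measurement. The issue is death without documented progression, however documented.
- *That the calculation measures bias from informative censoring.* It assumes independent hazards. It shows the effect of changing the endpoint from progression-or-death to progression alone, at assumed shares. The result is an overstatement only relative to a duration that ends at death.
- *That any difference from PFS is a contradiction.* Durations of response and CR start at response and cover responders only, so they may differ from PFS. The comparison bites mainly for stable disease.

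It is also fair that entry criteria describe all patients while responders are a selected group, and that regular imaging limits how many deaths go undocumented. Materiality is modest: safety is the primary objective, no p-values are calculated, the durations are summarised only if appropriate, and deaths are listed separately.

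**Conclusion.** The point holds in limited form. All three definitions omit death and lack a censoring rule while being assigned to Kaplan-Meier. Read literally, a death without documented progression is a non-event that can only be censored, and the reported durations tend to be longer than if death counted.

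How much longer cannot be established from the documents. The increases of 11%, 25% and 43% rest on exponential, independent times and on assumed shares of 10%, 20% and 30%; with no such deaths the effect is zero. ORR, PFS and OS do not change. A correction is worthwhile because these descriptive medians and rates are what will be reported on durability, but nothing here undermines the trial's primary objective.

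**What to change.** In SAP 6.1.2:

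1. End Duration of Overall Response, Duration of Overall CR and Duration of Stable Disease at the first of documented recurrence or progression (as applies to each) or death from any cause.
2. State one censoring rule, with its date, for patients who have no event.
3. Reconcile the SAP PFS rule (last objective progression-free assessment before new anticancer therapy) with the Visit 801 rule in protocol 9.2, so that PFS and the durations follow the same convention. While doing so, say whether symptomatic progression ends a response: PFS counts it, but the durations of response and CR require objective documentation.

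If a progression-only duration is really intended, the SAP should say so, state that deaths are censored and on what date, and report how many there were.

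The cost is a sentence or two per endpoint. No new data collection is needed, since PFS and OS already use death dates. Scheduled follow-up ends 30 ± 7 days after the last dose, so later deaths may be incompletely known, but that limit already applies to PFS and OS. The downside for the sponsor is that reported durations may be somewhat shorter.
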